9.4.10.2. Neutropenia

9.4.10.2.1. During Treatment (Periods 2 and 3)

During treatment with investigational product, patients with neutrophil counts <1500 cells/ μL ($<1.50 \times 10^3/\mu\text{L}$ or <1.50 GI/L) are to be managed for neutropenia as follows:

- <500 cells/ μL ($<0.50 \times 10^3/\mu\text{L}$ or <0.50 GI/L), see Discontinuation Criteria (Section 8.1)
- ≥ 500 cells/ μL and <1000 cells/ μL ($\geq 0.50 \times 10^3/\mu\text{L}$ and $<1.00 \times 10^3/\mu\text{L}$ or ≥ 0.50 GI/L and <1.00 GI/L), see Discontinuation Criteria (Section 8.1)
- ≥ 1000 cells/ μL and <1500 cells/ μL ($\geq 1.00 \times 10^3/\mu\text{L}$ and $<1.50 \times 10^3/\mu\text{L}$ or ≥ 1.00 GI/L and <1.50 GI/L), and the patient has a concurrent infection that requires systemic anti-infective therapy (for example, antibiotic, antifungal agent, antiviral agent):
 - The dose of investigational product is to be withheld, the patient is to receive appropriate medical care, and a repeat test for neutrophil count is to be performed within 4 weeks from knowledge of the initial report. If the repeat neutrophil count has returned to ≥ 1500 cells/ μL ($\geq 1.50 \times 10^3/\mu\text{L}$ or $\geq 1.50 \times 10^3/\mu\text{L}$) and the infection has resolved or is resolving, the patient may resume dosing of investigational product and evaluation at scheduled visits. If the neutrophil count remains ≥ 1000 cells/ μL and <1500 cells/ μL ($\geq 1.00 \times 10^3/\mu\text{L}$ and $<1.50 \times 10^3/\mu\text{L}$ or ≥ 1.00 GI/L and <1.50 GI/L), investigational product is to continue to be withheld and a repeat neutrophil count is to again be performed within another 4 weeks. If, after 2 repeat tests, the neutrophil count still remains ≥ 1000 cells/ μL and

<1500 cells/ μ L ($\geq 1.00 \times 10^3/\mu$ L and <1.50 $\times 10^3/\mu$ L or ≥ 1.00 GI/L and <1.50 GI/L), and:

- the infection has not fully resolved, the patient will be discontinued from the study treatment.
 - the infection has resolved, the patient may resume dosing and evaluation at scheduled visits. However, if resumption of dosing is not deemed appropriate by the investigator, the patient will be discontinued from the study treatment.
- ≥ 1000 cells/ μ L and <1500 cells/ μ L ($\geq 1.00 \times 10^3/\mu$ L and <1.50 $\times 10^3/\mu$ L or ≥ 1.00 GI/L and <1.50 GI/L), and the patient has no concurrent infection that requires systemic anti-infective therapy (for example, antibiotic, antifungal agent, antiviral agent):

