6.1.1. General Considerations for Analyses during the Blinded Treatment Dosing Period (Period 2)

Comparisons between ixekizumab regimen 80 mg Q4W and placebo will be performed for all analyses in Period 2.

Period 2 starts at the first injection of study treatment at Week 0 (Visit 2) and ends prior to the first injection of study treatment at Week 16 (Visit 8) or the ETV (between Weeks 0 and 16). If a patient has Visit 8 but does not receive injection at Week 16 (Visit 8), the last recorded time for Visit 8 is used as the end time for Period 2.

Baseline will be defined as the last available value before the first injection for efficacy, health outcome, and safety analyses. In most cases, this will be the measure recorded at Week 0 (Visit 2). For efficacy measures, if the patient does not take any injection, the last available value on or prior to randomization date will be used. Change from baseline will be calculated as the visit value of interest minus the baseline value. For safety analyses using a baseline period, the baseline period is defined as the time from Visit 1 to the date/time of the first injection.

The randomization to treatment groups is stratified by baseline CRP status (nonelevated versus elevated) and TNF inhibitors experience (experienced or naïve) as described in Section 5.2. Unless otherwise specified, the statistical analysis models will adjust for baseline CRP status, and prior TNF inhibitors experience(if applicable).

The primary analysis method for treatment comparisons of categorical efficacy and health outcomes variables at specific time points will be made using a logistic regression analysis with treatment, baseline CRP status, and TNF inhibitors experience (if applicable) in the model. The proportions, odds ratio and 95% confidence intervals (CIs) will be reported; treatment difference and 95% CIs will also be reported. Secondary analysis will be conducted using a Fisher's exact test. In the case when logistic regression model does not produce statistical results due to sparse data, Fisher's exact test will be used.

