6.11.2. Adverse Events

Adverse events (AEs) will be classified based upon the latest version of the MedDRA. Adverse events will be recorded at every study visit. Any condition starting on or after the date of informed consent will be considered an AE. Any preexisting condition which worsens in severity on or after the date of informed consent will be considered and recorded as an AE on the *Adverse Event (AE)* eCRF page from the date of worsening onwards.

A treatment-emergent adverse event (TEAE) is defined as an event that first occurred or worsened in severity after baseline and on or prior to the date of the last visit within the defined treatment period. Both the date/time of the event and the date/time of the dose (that is, injection) are considered when determining TEAEs. Treatment-emergent AEs will be assigned to the study period to which it's considered treatment-emergent:

- The MedDRA lowest level term (LLT) will be used when classifying AEs as treatment-emergent.
- The maximum severity recorded for each LLT prior to the first dose date/time in the treatment Period will be used as the pre-treatment severity for that LLT. If an event during the baseline period has missing severity, and the event persists during the treatment period, then it will be considered as treatment-emergent, regardless of the postbaseline level of severity. Events with a missing severity during the treatment period will be considered treatment-emergent.

- AEs with a particular LLT will be classified as treatment-emergent if they first start on or after the first dose date/time in the treatment period (ie, a patient has no preexisting conditions with that lowest level term), or if the severity is greater than the pre-treatment severity for that lowest level term. If a partial AE start date/time is present, the date/time will be compared as far as possible to the treatment start date/time in order to determine whether the event is treatment-emergent or not. If there is any doubt, the event will be flagged as treatment-emergent.

A follow-up emergent adverse event (FEAE) is defined as an event that first occurred or worsened in severity after the date of Visit 17 (that is, Week 52) or the ETV:

- The MedDRA LLT will be used when classifying AEs as follow-up emergent.
- For AEs that are ongoing at the date of Visit 17 or ETV, the maximum severity recorded for each LLT on or prior to the date of Visit 17 or ETV will be used as the follow-up baseline severity for that LLT.

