	Evaluation of Drug-Induced Serious Hepatotoxicity (eDISH) plot: use maximum ALT measurement and maximum total bilirubin measurement with patients having at least one postbaseline ALT and total bilirubin, which contributes one point to the plot. The measurements do not need to be taken at the same blood draw.	Period 2: eDISH plot (to be prepared in Spotfire)
Cytopenias	Cytopenias are defined using the PTs from the following 2 sub-SMQs of the Haematopoietic cytopenias SMQ (20000027) as specified in MedDRA: 
 • Broad and narrow terms in the Haematopoietic leukopenia (20000030) • Broad and narrow terms in the Haematopoietic thrombocytopenia (20000031) 	Period 2 (Fisher's exact test) and Period 3 (Summary): Combined Periods 2 and 3 (Summary): TEAE by PT within sub-SMQ Listing: TEAE (included in the same listing with hepatic, depression and interstitial lung disease AESIs)
Infections	Infections are events including all infections (defined using all the MedDRA PTs from the Infections and infestations SOC), serious infections, potential opportunistic infections, and infections resulting in anti-infective medication administration (i.e. antibacterial, antivirals, antifungals, antiparasitic treatments).	Period 2 (Fisher's exact test), Period 3 (Summary), Combined Periods 2 and 3 (Summary): SAE by PT
	Anti-infective medications are defined in LY2439821 PSAP v8 Appendix 5 (or most current version) including antibiotics, antifungals, antivirals, or antiprotozoals. Listing of patients experiencing a TEAE of infections will be provided including the following additional information: anti-infective medications use (if treated) with medication start/end dates, indication for use, and route; minimum postbaseline value within treatment Period 2 for leukocytes, platelets, lymphocytes, and absolute neutrophils.	Listing: TEAE with anti-infective medications.

Special Safety Topic	Definition / Derivation	Analysis / Summary / Listing

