	
The list of MedDRA terms used to identify infections that are predefined as potential OIs are found in the LY2439821 PSAP v8 Appendix 10 (or most current version). This list contains PTs as contained within categories (narrow or broad) from the Infections and infestations SOC and the Investigations SOC which can assist in identifying potential OIs. The narrow terms are considered OIs unless medical review determines that the reported term is not consistent with the patient's clinical history/presentation/course. Medical review of broad terms is needed for final determination of patients meeting the program definition of OIs.
 
Listing of patients experiencing a TEAE of OIs will be provided including the following additional information: type of infection, causative pathogen(s) identified through laboratory testing (Yes/No).
	
Period 2 (Fisher's exact test) , Period 3 and Combined Periods 2 and 3 (Summary): TEAE of OIs by maximum severity by PT
 
Listing: TEAE of OIs

	
The duration of each common ($\geq 1\%$ of total ixekizumab) TEAE PT of Infections, and duration of narrow terms for Opportunistic infections are defined as: Duration of treatment-emergent AE Infections (in weeks) = (End date of AE – Start date of AE + 1) / 7. Only TEAEs of infections beginning during treatment Period 2 or Period 3 will be included in the summary. If an AE has not ended by the date of completion of the treatment periods 2 or 3, or date of early discontinuation, it will be censored as of that date (last visit within the treatment period 2 or treatment period 3, or date of early discontinuation). If a patient has multiple episodes of the same TEAE, the episode with the greatest severity will be used for the duration of event calculation. If a patient has multiple episodes of the same TEAE with the same severity, the episode with the longest duration will be used for the duration of event calculation.
	
Period 2 (Summary): Duration of Common TEAE – Infections

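### The SAP's infection listing has no stated period limit but carries only Period 2 blood-count minima, so infections starting in Period 3 would be shown against earlier-period counts

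*SAP*

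**What the plan says.** In the Infections rows of Table RHCH.6.7 (SAP 6.11.3.1), the definition column states: "Listing of patients experiencing a TEAE of infections will be provided including the following additional information". The items that follow are anti-infective medication details and the "minimum postbaseline value within treatment Period 2 for leukocytes, platelets, lymphocytes, and absolute neutrophils". The matching entry in the analysis column reads only "Listing: TEAE with anti-infective medications" and names no period.

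Elsewhere in the same rows, infections are handled beyond Period 2. Serious infections are to be tabulated under "Period 3 (Summary), Combined Periods 2 and 3 (Summary): SAE by PT", as well as in Period 2. The derivation of infection duration says "Only TEAEs of infections beginning during treatment Period 2 or Period 3 will be included in the summary".

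SAP 6.11.2 adds the general rule: "Treatment-emergent AEs will be assigned to the study period to which it's considered treatment-emergent". SAP 6.1.1 closes Period 2 before the Week 16 injection, and Protocol 7.1 gives placebo-start patients their first ixekizumab at that injection.

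SAP 6.11.4.1 covers leukocytes, neutrophils, lymphocytes and platelets, the same four counts. For its shift tables it takes the lowest non-missing postbaseline value separately in each study period.

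**The concern.** The listing and its laboratory column appear to cover different spans of time. The listing admits any treatment-emergent infection, while the counts beside it stop at Week 16. A placebo-start patient whose infection begins between the Week 28 and Week 32 visits would be listed with the lowest count recorded on placebo, and neither the Week 28 nor the Week 32 result would be shown.

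Infections and cytopenias are both adverse events of special interest (Protocol 9.2.2). The protocol also links them. Its neutropenia rules in 9.4.10.2.1 apply in Periods 2 and 3 alike, and for counts from 1000 to below 1500 cells/μL they depend on whether the count is in that range "and the patient has a concurrent infection that requires systemic anti-infective therapy". No other output described in the SAP sets infections, anti-infective use and count minima side by side for each patient. What is at stake is whether that one output can do its job for Period 3.

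**Working it through.** The plan gives no figure to reproduce here. The check is a comparison of texts, a count of scheduled draws, and the share of planned time that falls outside the laboratory window.

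**1. Scheduled postbaseline hematology (Protocol Section 2).**
- Period 2: Weeks 4, 8, 12 and 16, which is 4 draws.
- Period 3: Weeks 20, 24, 28, 32, 36, 44 and 52, which is 7 draws, plus the early termination visit.
- Share outside the listing's window: 7 / (4 + 7) = 64%.

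**2. Draws on ixekizumab that the window can hold for placebo-start patients.** Period 2 ends before their first ixekizumab injection, so the number is 0 of 4. With a minimum taken within the period of the infection, a Period 3 infection would be shown against up to 7 scheduled draws, all scheduled after that first injection.

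**3. Planned treatment time.** Inputs: Period 2 of 16 weeks and Period 3 of 36 weeks (Protocol synopsis); 70 evaluable patients per arm (Protocol 5.2).
- Period 3 share of all treatment time: 36 / 52 = 69%. In patient-weeks, (140 × 36) / (140 × 52) = 5,040 / 7,280 = 69%.
- Period 3 share of ixekizumab time, no dropout: Period 2 gives 70 × 16 = 1,120 and Period 3 gives 140 × 36 = 5,040, so 5,040 / 6,160 = 82%.
- Same share if 10% of patients did not enter Period 3 (illustrative assumption, full Period 2 exposure): 0.9 × 5,040 = 4,536, and 4,536 / (4,536 + 1,120) = 80%.

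**4. Does the table mark Period 2-only outputs?** Sometimes. The eDISH plot and the summary of infection duration both carry a Period 2 label. The infection listing does not. The table's listing entries in general carry no period label, so the missing label does not settle the intent, but nothing other than the laboratory window points to a Period 2 listing.

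**5. The two rules for the same counts.** 6.11.4.1 takes the minimum per study period. The infection listing takes the Period 2 minimum whatever the period of the infection. No reason is given for the difference.

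**The case against.** The strongest reply is that the SAP never says the listing extends into Period 3. The only period named in its description is Period 2, so it may have been meant as a Period 2 listing. The Period 3 and combined labels belong to a different output, the table of serious infections. The sentence about infections beginning in either period belongs to a duration derivation whose planned output is itself Period 2 only. This stands as a limit on certainty: the span is inferred from the absence of a restriction. It does not rescue the wording. On that reading the listing needs a label, and Period 3 infections have no listing with matching counts.

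The second reply is that little is lost, and this also stands. Period 3 minima appear in the shift tables (6.11.4.1), abnormal leukocyte and platelet results are listed by patient (6.11.4), and all adverse events are listed by patient (6.11.2). A reviewer could join these by hand.

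The third is that SAP 6.11.3.1 lets the program safety analysis plan supersede this table. That document is not available here and may already resolve the point.

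A reader might go further and infer that the listing could conceal or create a link between cytopenia and infection, or that it bears on withholding or stopping drug. The documents do not support that. Under Protocol 9.4.10.2.1 those decisions are made during treatment from repeat counts, not from a report listing. Infection status enters the rule only in the 1000 to below 1500 band; the lower bands in Protocol 8.1.1 carry no infection condition. A reader might also take 82% to mean that about four in five infections on ixekizumab would be mismatched. That would need a constant infection rate, which the documents do not give.

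**Conclusion.** The wording should be corrected. As written, the listing is open to infections in either treatment period while its count minima come from Period 2 alone, in conflict with the per-period rule in 6.11.4.1. For an infection starting in Period 3, none of the seven scheduled draws of that period can appear. For placebo-start patients every count shown precedes ixekizumab.

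The time affected is 69% of planned treatment time, or 82% of planned ixekizumab exposure on the assumptions of 70 per arm and no dropout. The number of infections affected cannot be derived from the documents. The consequence is limited to one descriptive safety listing. No hypothesis test, summary table or efficacy result changes. What is missing is a planned by-patient view that puts a Period 3 infection next to the counts of that period. The conclusion rests on reading the listing as unrestricted, and on the program safety analysis plan not having already replaced this row.

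**What to change.** In the Infections row of Table RHCH.6.7, replace the Period 2 restriction on the count minima with: *within the treatment period in which the infection started*. This brings the listing into line with 6.11.4.1. If a Period 2 listing is what the sponsor wants, label it so and add a Period 3 listing built the same way. Check the current program safety analysis plan for the same wording and align it.

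Showing the last count on or before the infection start date would also help the reader, but it is optional.

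The cost is one line of SAP text and a change of period key in the listing program (a date join if the optional value is added). All the data are already collected.

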6.11.3.2. Anterior Uveitis

At each study visit, study health care providers will evaluate the patient for any symptoms of anterior uveitis. The incidence of anterior uveitis is identified using the preferred term 'iritidocyclitis'. The incidence rate of anterior uveitis will be summarized for patients with or without prior anterior uveitis separately, for the following study periods and analysis populations:

- Period 2 (Safety Population)
- Period 3 (Extended Treatment Period Population)

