
Secondary
 
The major secondary objectives are:
 
 To compare ixekizumab 80 mg Q4W to placebo in overall study population at Week 16 
Other secondary objectives are:
 
 To compare ixekizumab regimen 80 mg Q4W to placebo during the 16-week placebo-controlled period (Period 2) in overall study population 	
 Proportion of patients achieving an ASAS40 response Proportion of patients achieving an ASAS20 response Change from baseline in Ankylosing Spondylitis Disease Activity Score (ASDAS) Change from baseline in Bath Ankylosing Spondylitis Disease Activity Index (BASDAI) Change from baseline in Bath Ankylosing Spondylitis Functional Index (BASFI) Proportion of patients achieving ASDAS < 2.1 Change from baseline in magnetic resonance imaging (MRI) of the spine (Spondyloarthritis Research Consortium of Canada [SPARCC] score) Change from baseline in Short Form 36 (SF-36) physical component score (PCS) Proportion of patients who achieve ASAS20, ASAS40, ASAS 5/6, and partial remission by ASAS criteria Change from baseline in the individual components of the ASAS criteria Change from baseline in BASDAI Proportion of patients reaching BASDAI50 Change from baseline in ASDAS Proportion of patients who experience clinically-important improvement (change of ASDAS from baseline ≥ 1.1) or major improvement (change of ASDAS from baseline ≥ 2.0 or achievement of the lowest possible score) or inactive disease (ASDAS score < 1.3) Change from baseline in the measure of high sensitivity C-reactive protein (CRP) Change from baseline in BASFI Change from baseline in mobility 
 Bath Ankylosing Spondylitis Metrology Index (BASMI) (linear) and individual components Chest expansion Change from baseline in occiput to wall distance

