
 To determine if the effect of ixekizumab is maintained through Week 52 To measure ixekizumab exposure and assess the relationship between exposure and immunogenicity 	
 Change from baseline in MRI of the SIJ (SPARCC score) Change from baseline in Maastricht Ankylosing Spondylitis Enthesitis Score (MASES) Incidence rate of anterior uveitis or uveitis flares Change from baseline in the following health outcomes measures: Functional Assessment of Chronic Illness Therapy (FACIT) Fatigue Scale, Work Productivity Activity Impairment–Spondyloarthritis (WPAI-SpA) scores, and SF-36 (both PCS and mental component scores [MCS]) and Quick Inventory of Depressive Symptomatology–Self Report 16 items (QIDS-SR16) score 
All endpoints assessed at Week 16 (above) and during the 16-week placebo-controlled period (above) will continue to be assessed through Week 52.
 
In addition, the following endpoint is added:
 
 NSAID intake (ASAS-NSAID score and % of patients taking NSAIDs) Serum trough concentrations of ixekizumab Ixekizumab serum trough concentrations associated with ADA titer sub groups

Exploratory
 
 To evaluate time to first response To compare ixekizumab regimen 80 mg Q4W to placebo during the 16-week placebo-controlled period (Period 2) To evaluate the incidence of anti-ixekizumab antibodies and their relationship to the efficacy of ixekizumab 	
 Onset of action and treatment response (ASAS, ASDAS, CRP, BASFI) during the placebo-controlled period Change from baseline in SPARCC SIJ Structural Score (SSS) Change from baseline in ASAS HI score Efficacy response rates listed below at Weeks 16 and 52 by treatment-emergent anti-drug antibody (TE-ADA) status and by neutralizing anti-drug antibody (NAb) status: 
 Proportion of patients achieving ASAS40 Proportion of patients achieving ASAS20 Proportion of patients achieving ASDAS inactive disease

Note: Other exploratory objectives and endpoints will be specified in the statistical analysis plan (SAP).
	

5. Study Design

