9.4.6. Ocular Examination

At each study visit, investigator or study health care providers will evaluate the patient for any symptoms of anterior uveitis as specified in the Schedule of Activities (Section 2). If the patient develops eye pain or discomfort, eye redness, blurring of vision, or any other symptoms suggestive of anterior uveitis, the patient must be evaluated by an ophthalmologist. The ophthalmologist diagnosis is completed in the CRF.

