6.11.3.1. Special Safety Topics including Adverse Events of Special Interest

Safety information on special topics including AEs of special interest (AESI) will be presented by treatment group and by study period. [Table RHCH.6.7](#) provides the definitions/derivations and analyses methods (including analyses, summaries and by-patient listings) of special safety topics including AESIs.

Potential AESIs will be identified by a standardized MedDRA query (SMQ) or a Lilly-defined MedDRA PT listing. Preferred terms within an SMQ will be classified as broad and narrow. In the Lilly-defined MedDRA PT listings, Lilly has provided the broad and narrow classification. The Lilly-defined broad terms are for a more sensitive search of potential events of interest and the Lilly-defined narrow terms are for a more specific search. Therefore, the summaries will include the classifications of broad term (same as pooling narrow and broad terms together) and narrow term.

In the event that the listing of terms or analysis changes for a special safety topic, it will be documented in the program safety analysis plan (PSAP) which will supersede this document; it will not warrant an amendment to the individual study SAP. For final analysis, the most current version of PSAP will be used, including PSAP released after SAP finalization but before database lock.

For Period 3, summaries will be provided for the Extended Treatment Period Population. In addition, for Combined Periods 2 and 3 on ixekizumab treatment only, selective summaries will be provided for the All Ixekizumab Exposures Safety Population.

In general, AESI summary will not be provided for Follow-Up Population during Period 4 except hepatic laboratory tests.

Table RHCH.6.7. Definitions and Analyses of Special Safety Topics including Adverse Events of Special Interest

Special Safety Topic	Definition / Derivation	Analysis / Summary / Listing

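### The uveitis endpoint is counted from one misspelt preferred term and does not use the ophthalmologist diagnosis recorded in the CRF

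*SAP*

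**What the plan says.** Protocol Section 4 (Table RHCH.1) lists "Incidence rate of anterior uveitis or uveitis flares" among the other secondary endpoints, and the SAP's Study Objectives table repeats it. The objective it serves is "To compare ixekizumab regimen 80 mg Q4W to placebo during the 16-week placebo-controlled period (Period 2) in overall study population".

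Protocol Section 9.4.6 describes how episodes are found. Patients are checked for symptoms at each visit. If any suggest anterior uveitis, "the patient must be evaluated by an ophthalmologist", and "The ophthalmologist diagnosis is completed in the CRF".

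SAP Section 6.11.3.2 gives the derivation. "The incidence of anterior uveitis is identified using the preferred term" is followed by a single term, "iritidocyclitis". The incidence rate "will be summarized for patients with or without prior anterior uveitis separately", in Period 2 (Safety Population) and Period 3 (Extended Treatment Period Population).

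**The concern.** The endpoint and the counting rule have different scope. The endpoint names anterior uveitis and flares. The rule names one dictionary term, does not say what a flare is, and does not mention the specialist diagnosis that the protocol arranges to collect. Under such a rule, whether an episode counts depends on how its verbatim text was coded and not on whether an ophthalmologist confirmed it.

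At stake is whether a stated secondary endpoint can be reproduced from the SAP and whether it captures the episodes it is meant to capture. Patients who can flare are eligible: past uveitis is a qualifying feature in Protocol Appendix 5, and exclusion criterion [14] removes only those with active disease in the 4 weeks before randomization.

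**Working it through.** The plan gives no figure to reproduce here: no expected uveitis rate and no power for this endpoint. The check sets the sections side by side.

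1. **Scope of the endpoint.** Protocol Section 4 and the SAP objectives agree that it covers anterior uveitis or flares.

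2. **Scope of the rule.** SAP Section 6.11.3.2 uses one preferred term. No other SAP section fills the gap: the endpoint is absent from the list in Section 6.9.4 and from Table RHCH.6.4.

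3. **Spelling.** The term is printed "iritidocyclitis"; the ordinary spelling is iridocyclitis.

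4. **Data collected against data used.** The Schedule of Activities has eye symptoms assessed at every visit from screening to Week 52 and at early termination, and Protocol Section 9.4.6 puts the ophthalmologist diagnosis in the CRF. SAP Section 6.11.3.2 repeats the symptom check but does not refer to the diagnosis.

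5. **How an episode reaches the count.** Protocol Section 9.2 has sites record new or changed conditions as adverse events. SAP Section 6.11.2 treats any condition starting on or after consent, or any worsening of a preexisting one, as an adverse event. A diagnosed episode should therefore be reported and coded. It then enters the endpoint only if the code is the named term.

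6. **What happens otherwise.** An episode coded to another term is outside the endpoint but not lost from the database. SAP Section 6.11.2 plans summaries by preferred term and a by-patient listing of all adverse events.

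7. **Flares.** The section defines none, but it reports patients with and without prior anterior uveitis separately. Given exclusion criterion [14], an on-study episode in the first group is in practice a recurrence, and one in the second group is new onset. Both are still found through the same single term.

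8. **Contrast within the SAP.** For adverse events of special interest, "Potential AESIs will be identified by a standardized MedDRA query (SMQ) or a Lilly-defined MedDRA PT listing". In Table RHCH.6.7, inflammatory bowel disease has five narrow terms plus a broad list, and interstitial lung disease has an SMQ plus six added terms. Section 6.11.3.1 also lets a later program safety analysis plan update term lists for special safety topics. Uveitis has its own section outside that table, with no reference to that plan.

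9. **Scale.** Protocol Section 5.2 expects 70 evaluable patients per group. One event is 1/70 = 0.0143, or 1.4 percentage points. This is the weight of one event in a full arm, not an estimate of events missed. The weight would be greater within the prior-uveitis group, whose size is not given.

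**The case against.** The strongest reply is that nothing need be missed. A preferred term gathers many lower level terms, so if all the usual ways of writing anterior uveitis code to the intended term, one term is a complete definition. A narrow term may also be deliberate in a section about anterior uveitis. The dictionary is not in the documents, so under-counting cannot be demonstrated. This stands, and it limits the point to what the rule permits. It does not rescue the rule, because the SAP neither shows that the term is exhaustive nor provides a check against the diagnosis that would reveal a gap.

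Three stronger readings are tempting, and the documents do not support them:

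- **The ophthalmologist diagnosis is lost.** Protocol Section 9.2 and SAP Section 6.11.2 give it a route into coded adverse events. What is missing is direct use of the diagnosis, or a reconciliation with it.
- **Flares are ignored.** The split by prior anterior uveitis largely separates recurrence from new onset. What is missing is a statement that this is how flares are identified.
- **The misspelling produces zero events in both arms.** That needs a literal match on a printed slip. Terms are assigned by dictionary coding, so a programmer would have to select an existing term. The error should be corrected but is minor on its own.

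It can also be said that preferring a CRF diagnosis to coded events is a matter of taste. That is only partly right: as written, the rule excludes an ophthalmologist-confirmed episode if its code differs, which is more than a question of wording.

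**Conclusion.** The point holds in limited form. SAP Section 6.11.3.2 is narrower than the endpoint it derives, and it leaves unused a more direct source that the protocol already collects. Confirmed episodes coded to another term would be left out of the endpoint while remaining visible in the general adverse event tables and listings.

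The size of any under-count cannot be estimated. A reader might infer that the endpoint will certainly be under-counted, or most of all in patients with prior uveitis; the documents hold no rate, stratum size or coding information to support either. The conclusion assumes that the rule will be applied as written and that the CRF diagnosis can be retrieved for analysis, as Protocol Section 9.4.6 implies.

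The consequence is contained. SAP Section 6.4 makes no multiplicity adjustment outside the primary and major secondary outcomes, and the primary analysis, the sample size and the alpha allocation are untouched. The change is worth making before database lock because it costs little.

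**What to change.** In SAP Section 6.11.3.2:

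- Define an event as an anterior uveitis episode after first dose that is confirmed by the ophthalmologist diagnosis in the CRF.
- Reconcile these episodes with adverse events coded to a prespecified, correctly spelled term list.
- State that episodes in patients with prior anterior uveitis are the flares and that those in patients without it are new onset.

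The cost is SAP wording, a small reconciliation step and slightly more programming. No new data collection is needed.
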